7.2.1 Analysis Populations.....	27
7.2.2 Primary Objective	27
7.2.3 Secondary Objective	28
7.2.4 Exploratory Objective.....	29
7.2.5 Safety Monitoring Plan.....	29
7.3 Data Management Plan.....	29
7.3.1 Research Electronic Data Capture (REDCap).....	29
7.3.2 Role of the CDC Investigators in the Project.....	30
8 HUMAN SUBJECTS	30
8.1 Human Participants Involvement, Characteristics, and Design	30
8.2 Sources of Material.....	31
8.3 Potential Risks and Benefits.....	31

8.4 Adequacy of Protection	31
8.4.1 ClinicalTrials.gov Requirements	31
9.0 HUMAN SUBJECTS.....	31
9.1.1 Vulnerable Subjects.....	31
9.1.2 Vulnerable Subjects Research	32
REFERENCES	33

PROTOCOL SUMMARY

Title:	A Prospective Observational Study to Evaluate the Safety of COVID-19 Vaccination in Children and Adolescents
Phase:	Phase 4
Population:	Up to 320 male or female children and adolescents \geq 5 years to < 16 years
Clinical Sites:	Four: Duke University (Lead); Cincinnati Children's Hospital (Contributing); Kaiser Permanente (Contributing); Columbia University (Contributing)
Study Duration:	24 months
Participant Duration:	Approximately 7 months
Description of Study Procedures:	
This is a prospective, observational study to evaluate the safety of COVID-19 vaccination in children and adolescents receiving vaccine as part of standard of care. Children and adolescents who have not received any previous COVID-19 vaccines will be enrolled with their first dose. Children and adolescents who have completed their primary vaccine series will enroll with their age-appropriate booster dose based on current FDA indications and CDC recommendations.
 
Injection-site (local) and systemic reaction data and unsolicited adverse events will be assessed on vaccination day and daily during the 7 days following each COVID-19 vaccination dose using either identical web-based or paper memory aids, depending on study participant preference.
 
At 3 sites, serum samples will be collected for optional assessment of antibody titers to COVID-19. Each participant who opts in will have baseline (within 3 days of vaccination) serologies obtained. Serum samples will also be collected for immunogenicity assessments at 28 (+7) days after dose 2 or a booster dose.
 
All participants will be followed for 181 days after the last study dose 2 or a booster dose for serious adverse events (SAEs) and adverse events of special interest (AESI).

Objectives:	
Primary Objective (PO): PO: To characterize the safety of authorized and recommended COVID-19 vaccines among children and adolescent participants

	
Secondary Objective (SO): SO: To assess the safety of simultaneous administration of COVID-19 vaccine with other routinely recommended vaccines among children and adolescent participants
 
Exploratory Objectives (EO):
 
EO 1: To assess adolescent and parent perceptions of the COVID-19 vaccine recommendations and experience with receipt of the vaccine
 
EO 2: To assess the safety of COVID-19 vaccine stratified by baseline COVID-19 serostatus (positive versus negative) in a subset of child and adolescent participants
 
EO 3: To assess adverse events of special interest through 6 months after dose 2 of COVID-19 vaccine or a booster dose
 
EO 4: To assess serious adverse events through 6 months after dose 2 of COVID-19 vaccine or a booster dose
 
EO 5: To assess immune responses to SARS-CoV-2 antigens after COVID-19 vaccine

Outcome Measures:	
Primary Outcome Measures (POM):
 
POM 1: Proportion of participants with defined local or systemic reactogenicity events (stratified according to severity and in total) on days 1-7 after each dose of COVID-19 vaccine
 
POM 2: Proportion of participants with at least one severe (Grade 3) solicited local or systemic reactogenicity event on days 1-7 after each dose of COVID-19 vaccine
 
POM 3: Proportion of participants with at least one moderate-to-severe (Grade 2-3) solicited local or systemic reactogenicity event on days 1-7 after each dose of COVID-19 vaccine
 
POM 4: Proportion of participants with an unsolicited adverse event on days 1-7 after each dose of COVID-19 vaccine
 
POM 5: Proportion of participants with an adverse event of special interest through 29 days after dose 2 of COVID-19 vaccine or a booster dose
 
POM 6: Proportion of participants with at least one serious adverse event through 29 days after dose 2 of COVID-19 vaccine or a booster dose and a description of the events
 
Secondary Outcome Measure (SOM):

	
SOM 1: Assessment of primary outcome measures 1-6 in those receiving other routinely recommended vaccines with each dose of COVID-19 vaccine versus those receiving COVID-19 vaccine alone
 
Exploratory Outcome Measures (EOM):
 
EOM 1: Proportion of participants and legal guardians/parents with negative or positive perceptions of the vaccination experience based on participants responses to individual questions on the perceptions questionnaire
 
EOM 2: Assessment of primary outcome measures 1-6 in those with positive baseline COVID-19 serostatus versus those with a negative baseline serostatus
 
EOM 3: Proportion of participants with an adverse event of special interest through 6 months after dose 2 of COVID-19 vaccine or a booster dose
 
EOM 4: Proportion of participants with a serious adverse event through 6 months after dose 2 of COVID-19 vaccine or a booster dose
 
EOM 5a: The proportion of participants seropositive to SARS-CoV-2 variants tested prior to and following mRNA COVID-19 vaccine in a subset of children and adolescents.
 
EOM 5b: The geometric mean ID₅₀ and ID₈₀ titers of neutralizing antibodies for each SARS-CoV-2 variant tested pre- and post-mRNA COVID-19 vaccine in a subset of children and adolescent participants.

Estimated Time to Complete Enrollment:	12 months

1 BACKGROUND

As of September 2022, there have been more than 95 million cases of COVID-19 leading to more than one million deaths in the United States (1). Although COVID-19 infection is generally milder in children than adults, it does cause significant pediatric morbidity and mortality. The American Academy of Pediatrics reports that 15 million children have been infected during the pandemic (2), leading to nearly 9000 cases of multisystem inflammatory syndrome in children (MIS-C) and 1500 deaths. From this perspective, safe and effective pediatric COVID-19 vaccines are needed to curb the pandemic.

In May 2021, the FDA issued an Emergency Use Authorization (EUA) for the Pfizer-BioNTech (Pfizer) mRNA COVID-19 vaccine in children aged 12-15. In the Phase III trial leading to the EUA, 2,260 adolescents 12-15 years old were randomized 1:1 to receive 2 doses of 30 ug of the BNT162b2 vaccine or placebo administered 3 weeks apart (3). Pain at the injection site was the most common local reaction, occurring in 86% of vaccine recipients after dose 1, and was somewhat less common after dose 2 (79%). Fatigue (60%), headache (55%), and chills (28%) were the most common systemic events after dose 1. These were slightly more common after dose 2 (fatigue (66%), headache (65%), and chills (42%).

On October 29, 2021 the FDA issued an EUA for the Pfizer-BioNTech vaccine in children aged 5-11 years old, administered as 2 doses of 10 ug 3 weeks apart. The main safety study randomized children 2:1 to BNT162b2 (N=1518) vaccine or placebo (N=750); children were followed for at least 2 months after dose 2. In general, children had less severe systemic reactions than adolescents and young adults following the age-appropriate dose. The most common systemic reactogenicity events in children aged 5-11 years after were fatigue (33.6-39.4%) and headache (22.4-28%). In children aged 5-11 years fever was infrequent after dose 1 (2.5%) and dose 2 (6.5%). There were no serious adverse events in the pediatric study that were considered related to the BNT162b2 study vaccine. No cases of myocarditis or anaphylaxis occurred in the study (4).

In June 2022 the FDA issued an EUA for the Moderna mRNA-1273 vaccine in children and adolescents. In the published phase III adolescent clinical trial 2,732 adolescents 12-17 were randomized 2:1 to receive 2 doses of 100 ug of the mRNA-1273 vaccine or placebo, 4 weeks apart (5). Pain was the most common local reaction, occurring in 94% of vaccine recipients after dose 1 and 93% after dose 2. The most common systemic reactions after dose 1 included fatigue (48%), headache (45%), myalgia and chills. Fatigue (68%) and headache (70%) were more common after dose 2.

Although these randomized controlled trials demonstrate the safety and immunogenicity of mRNA vaccines in children, there are several gaps in our current knowledge.

First, the initial clinical trials in adolescents excluded children with known history of COVID-19 infection. Baseline antibody testing was ascertained in both trials. Approximately 4% of participants in the Pfizer trial and 6% in the Moderna trial were seropositive at baseline, suggesting a prior history of asymptomatic infection. There were no significant differences in reactogenicity between children who were seropositive and those who were not. However, children with previous symptomatic infection may

have more robust reactogenicity, as has been seen in adults (6). The Pfizer 5-11 year-old trial did enroll children with prior COVID infections and found no significant differences in reactogenicity between children who did and did not have a prior history of infection (4).

Secondly, the published pediatric trials did not include a diverse population. COVID-19 infections, hospitalizations, and deaths disproportionately impact Black and Hispanic or Latinx populations (7). However, only 5% of participants in the Pfizer adolescent trial and 3% in the Moderna adolescent trial were Black. Similarly, only 12% of participants in each trial were of Hispanic or Latinx ethnicity. The Pfizer 5-11 year-old trial was slightly more diverse; 6.5% of participants were Black or African American and 21% were of Hispanic ethnicity (4).

Finally, there are sparse data regarding reactogenicity of COVID-19 vaccine when co-administered with other recommended vaccines. In all of the pediatric Phase III clinical trials to date, receipt of any vaccine within 7 days of enrollment was an exclusion criterion (8). The current CDC clinical considerations for COVID-19 vaccine do allow for receipt of COVID-19 vaccines on the same day as other vaccines. The guidance states that if multiple vaccines are administered at a single visit, each should be administered at a different injection site. (9). However, published data regarding the safety and reactogenicity of this approach are lacking.

In September 2022, the FDA amended the use of the Pfizer-BioNTech vaccine to authorize bivalent vaccine for individuals ≥ 12 year-old (10). However, there are no clinical data regarding the safety and immunogenicity of the BA.4 and BA.5 variant vaccines currently available in the United States.

Herein, we propose a prospective observational safety study of children receiving COVID-19 vaccine per standard of care, including booster doses. We hope to fill existing knowledge gaps concerning the safety of COVID-19 vaccines in the pediatric population by including children who were excluded from the trials, such as adolescents with a prior history of COVID-19 and those receiving concomitant vaccines. We also plan to make every effort to recruit a racially and ethnically diverse pediatric population.

2 STUDY OBJECTIVES

Primary Objective (PO):

To characterize the safety of authorized and recommended COVID-19 vaccines among children and adolescent participants

Secondary Objective (SO):

To assess the safety of simultaneous administration of COVID-19 vaccine with other routinely recommended vaccines among children and adolescent participants

Exploratory Objectives (EO):

EO 1: To assess adolescent and parent perceptions of the COVID-19 vaccine recommendations and experience with receipt of the vaccine

EO 2: To assess the safety of COVID-19 vaccine stratified by baseline COVID-19 serostatus (positive versus negative) in a subset of child and adolescent participants

EO 3: To assess adverse events of special interest through 6 months after dose 2 of COVID-19 vaccine or a booster dose

EO 4: To assess serious adverse events through 6 months after dose 2 of COVID-19 vaccine or a booster dose

EO 5: To assess immune responses to SARS-CoV-2 antigens after COVID-19 vaccine

Primary Outcome Measures (POM):

POM 1: Proportion of participants with defined local or systemic reactogenicity events (stratified according to severity and in total) on days 1-7 after each dose of COVID-19 vaccine

POM 2: Proportion of participants with at least one severe (Grade 3) solicited local or systemic reactogenicity event on days 1-7 after each dose of COVID-19 vaccine

POM 3: Proportion of participants with at least one moderate-to-severe (Grade 2-3) solicited local or systemic reactogenicity event on days 1-7 after each dose of COVID-19 vaccine

POM 4: Proportion of participants with an unsolicited adverse event on days 1-7 after each dose of COVID-19 vaccine

POM 5: Proportion of participants with an adverse event of special interest through 29 days after dose 2 of COVID-19 vaccine or a booster dose

POM 6: Proportion of participants with at least one serious adverse event occurring through 29 days after dose 2 of COVID-19 vaccine or a booster dose and a description of the serious adverse events

Secondary Outcome Measure (SOM):

SOM: Assessment of primary outcome measures 1-6 in those receiving other routinely recommended vaccines simultaneously with each dose COVID-19 vaccine versus those receiving COVID-19 vaccine alone

Exploratory Outcome Measures (EOM):

EOM 1: Proportion of participants and legal guardians/parents with negative or positive perceptions of the vaccination experience based on participants responses to individual questions on the perceptions questionnaire

EOM 2: Assessment of primary outcome measures 1-6 in those with positive baseline COVID-19 serostatus versus those with a negative baseline serostatus

EOM 3: Proportion of participants with an adverse event of special interest through 6 months after dose 2 of COVID-19 vaccine or a booster dose

EOM 4: Proportion of participants with a serious adverse event through 6 months after dose 2 of COVID-19 vaccine or a booster dose

EOM 5a: The proportion of participants seropositive to SARS-CoV-2 variants tested prior to and following mRNA COVID-19 vaccine in a subset of children and adolescents

EOM 5b: The geometric mean ID₅₀ and ID₈₀ titers of neutralizing antibodies for each SARS-CoV-2 variant tested pre- and post-mRNA COVID-19 vaccine in a subset of child and adolescent participants.

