4.4 Reasons for and Handling of Withdrawals

The following may be reasons for study withdrawal:

- As deemed necessary by the principal investigator (PI).
- Parent(s)/LAR(s) withdrawal of permission for their child to participate.
- Subject withdrawal of assent (based on site IRB requirements)
- Lost to follow-up.
- Termination of the study by the sponsor.

A parent/LAR may withdraw permission for their child to participate at any time and for any reason, without penalty. Data collected prior to withdraw in the study will be included in the study.

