5 STUDY SCHEDULE, PROCEDURES, & EVALUATIONS

5.1 Schedule of Events

Children and adolescents meeting the proposed eligibility criteria (**Section 4.0**) will be recruited. Written informed consent will be obtained from study participants or their parent/guardian and assent from participants per local IRB requirements prior to conducting any study procedures. **Table 1** describes the schedule of study visits for children enrolling with their first COVID dose.

Table 1: Schedule of events: Primary Series (Dose 1 and 2)		Visit 1	Visit 1a	Visit 2	Visit 2a	Visit 3	Visit 4
Procedure	Type of contact	Clinic	Phone/Text /Email/Data Review a, b	Phone/Data Review c	Phone/Text/Email/Data Review a, b	Clinic/Phone d	Phone/Data Review
Time Relative to 1st COVID-19 Vaccine	1 (-3)	1-7 (+3)					
Time Relative to 2nd COVID-19 Vaccine			1 (+3)	1-7 (+3)	29 (+ 7)	181 (+/- 7)	
Informed consent & Medical Release of Information	X						
Review Eligibility Criteria	X						
Data Collection (Demographic information and Medical History)	X						
COVID-19 Vaccination History	X						
COVID-19 Disease History	X	X	X	X	X	X	
Concomitant Medications and Vaccines	X	X	X	X	X	X	
Standard of Care COVID-19 Vaccine	X		X				
Memory aid training + supplies (training on temperature)	X		X				
Blood draw ^e	X ^f				X		
Staff to review Memory aid form (REDCap or paper)		X	X	X			
Obtain solicited adverse events		X	X	X			
Obtain unsolicited adverse events		X	X	X			
Obtain serious adverse event information and AESIs		X	X	X	X	X	
Obtain parental and adolescent perceptions of COVID vaccine recommendations and receipt ^g		X		X			
Confirm date of next vaccine	X	X					
Confirm next study visit	X	X	X	X	X	X	

a. Memory aid (solicited local and systemic reactogenicity events) to be completed by LAR/participant on Days 1-7 after vaccination.

b. LAR/Participants completing paper diary only will be called 3 [+3] days after each dose of vaccine as a reminder and to prompt to bring paper diary to next visit

c. May be clinic visit if COVID vaccine is administered at research site

d. May be phone visit if not obtaining immunogenicity labs

e. Blood draws are optional and will be only performed at participating sites

f. Blood draw may be performed 3 days before or after vaccine

g. Adolescent perceptions of COVID-19 vaccine will be collected for adolescents (ages 12 - < 16 only)

Visit 1, Day of Vaccine or up to 3 Days Prior - Screening, Enrollment, and Vaccination (Clinic Visit)

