- Obtain parental permission by written informed consent and a release of medical record information, based on site IRB requirements
- Obtain assent from child, based on site IRB requirements
- Review and confirm study eligibility
- Obtain information on preferred method of contact for follow-up (telephone or email, or text reminder reminder)
- Obtain demographic data & COVID-19 vaccine history
- Obtain history of vaccines within 2 weeks of enrollment
- Obtain medical history, including COVID-19 disease history
- Obtain concomitant medication and vaccine use
- For children at participating sites, obtain optional blood sample within 3 days before or after vaccination for serologic analysis
- Dispense thermometer, ruler (in order to standardize measurements) and memory aid. Review instructions for use of thermometer, ruler, and memory aid completion. Preference will be to complete the memory aid electronically, with paper as a back-

up.

- Confirm anticipated date of COVID vaccine, if not already occurred
- Confirm date of next scheduled study visit

Visit 1a, Days 1-7 after dose 1 (Phone Visit)

- Subjects/parent/LAR will complete their memory aid via paper or electronic entry at approximately the same time each day for days 1-7, study staff will review subject-entered data within the database or by phone contact
- For participants using REDCap web-based system:
 - Study staff will send daily reminders to fill out the symptom diary
 - Record clinical data related to COVID diagnoses
 - Study staff will review REDCap system to confirm data capture and assess for any AE, AESIs, or SAEs on day 3 and 7 after vaccine
 - If any missing values, reported hives, or Grade 3 events occurred, the study staff will use phone contact to gather more information
 - The first parental and adolescent (if applicable) survey will be administered on day 7 after vaccine
 - Study staff will verify date of next COVID-19 vaccine and remind subjects to complete memory aid with next dose
- For participants using paper diary:
 - Study staff will call participants on day 3 after vaccine as a reminder to fill out the symptom diary
 - The first parent and adolescent (if applicable) survey will be administered on day 7
 - Study staff will call participants on day 7 (+ 3 days)
 - Record symptom diary
 - Record COVID-19 diagnoses
 - Record first parental and adolescent (if applicable) survey
 - Verify date of next COVID-19 vaccine and remind subjects to complete memory aid with next dose

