Visit 2, COVID-19 Vaccine Dose 2 (+ 3 Days) (Clinic or Phone Visit)

- Confirm receipt of second dose of COVID vaccine
- Record any AEs, AESIs, SAEs, and concomitant medications and vaccinations as described in **Section 5.5**.
- Record clinical data related to COVID-19 diagnoses
- Confirm preferred method of contact for follow-up (telephone, email, or text reminder)
- Review instructions for use of thermometer, ruler, and memory aid completion.

Visit 2a, Days 1 - 7 Days after dose 2 (Phone Visit)

- Subjects/parent/LAR will complete their memory aid via paper or electronic entry at approximately the same time each day for days 1-7, study staff will review subject-entered data within the database or by phone contact
- For participants using REDCap web-based system:
 - Study staff will send daily reminders to fill out the symptom diary
 - Record clinical data related to COVID diagnoses
 - Study staff will review REDCap system to confirm data capture and assess for any AE, AESIs, or SAEs on day 3 and 7 after vaccine

- If any missing values, reported hives, or Grade 3 or greater events occurred, the study staff will use phone contact to gather more information
- The second parental and adolescent (if applicable) survey will be administered on day 7 after vaccine
- For participants using paper diary:
 - Study staff will call participants on day 3 after vaccine as a reminder to fill out the symptom diary
 - The second parental and adolescent (if applicable) survey will be administered on day 7 after vaccine
 - Study staff will call participants on day 7 (+ 3 days) after vaccine
 - Record symptom diary
 - Record COVID-19 diagnoses
 - Record second parental and adolescent (if applicable) survey

Visit 3, 28 Days (window days 29-35) after COVID-19 Dose 2 (Clinic Visit or Phone Visit)

- Clinic visit for optional post-vaccination blood draw for immunogenicity studies
- If no blood draw, may be a phone visit
- Review concomitant medications and vaccinations.
- Solicit for the occurrence of any adverse events of special interest or serious adverse events.

Visit 4, 180 days (window Days 174 - 188) after Dose 2 (Phone Visit)

- Record any SAEs or adverse events of special interest as described in **Section 5.5**
- Obtain concomitant medication and vaccine use

Table 2 describes the schedule of study visits for children enrolling with their COVID-19 booster dose.

Table 2: Schedule of events: Booster Dose

Procedure	Visit 1	Visit 1a	Visit 2	Visit 3

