5.3 Demographic Information, Medical History, Immunization History

The participant's age, race/ethnicity, and medical history will be obtained by parent/guardian report at the time of enrollment. The participant's medical history, concomitant medications and vaccines taken within 2 weeks of enrollment will be obtained by review of the electronic health record (EHR) and will be reviewed and confirmed by the parent/guardian at the time of enrollment.

Vaccines received during the study period will be documented by the clinic or research staff who administered the vaccines. Documentation will include: product brand, lot number, site and date/time of vaccine administered during study participation.

Throughout the study, the medical record will be reviewed to assess and record the occurrence of any serious adverse events or adverse events of special interest that occurred during the period of study enrollment.

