7.2 Analysis Plan

7.2.1 Analysis Populations

There will be one study population named the Study Cohort. The Study Cohort includes any participant that was enrolled and received at least one dose of a COVID-19 vaccine.

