8.2 Sources of Material

Medical history and immunization history will be obtained from the medical record and from parent and patient report. Demographic information will be obtained from the medical record and parent/LAR and patient report. Participants will record solicited adverse reactogenicity events and any medical intervention sought on the day of and 7 days following both vaccinations on the memory aid. Memory aid captured information will be reported to the study team during a telephone call or in the web-based REDCap system. Information about SAEs and AESIs will be obtained through medical record review and visits.

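### A child enrolled at dose 1 who never receives dose 2 has no scheduled SAE/AESI contact after Day 7 (+3), and the plan sets no end date for that child's safety windows

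*Combined protocol and SAP*

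**What the plan says.** **Outcome windows.** Section 2 defines POM 5 as the proportion with an "adverse event of special interest through 29 days after dose 2 of COVID-19 vaccine or a booster dose". POM 6 uses the same limit for SAEs, and EOM 3 and 4 run to 6 months from the same anchor. The POM 5/6 table in Section 7.2.2 repeats it.

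**Visit schedule.** In Table 1 (Section 5.1), only Visits 1 and 1a are timed from dose 1. Visits 2, 2a, 3 and 4 fall under the row "Time Relative to 2nd COVID-19 Vaccine", and the visit descriptions agree. SAE/AESI information is collected at Visits 1a, 2, 2a, 3 and 4. At Visit 1a, "Study staff will verify date of next COVID-19 vaccine and remind subjects to complete memory aid with next dose". Visit 2 opens by confirming that dose 2 was received.

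**Other limits in Section 5.5.** The end of study and the release for unscheduled-visit records are counted from the second dose. The surveillance period is counted from the second dose or a booster.

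**Who is followed.** Section 3.1 follows participants to Day 181 for SAEs and AESIs and names no dose. The Protocol Summary refers to all participants but counts their 181 days from dose 2 or a booster. Section 7.2.1 states: "The Study Cohort includes any participant that was enrolled and received at least one dose of a COVID-19 vaccine". Section 4.4 lists reasons under "The following may be reasons for study withdrawal". Missing dose 2 is not among them, although investigator discretion is.

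**Record review.** Section 5.3 provides for review throughout the study to find "serious adverse events or adverse events of special interest that occurred during the period of study enrollment". Section 8.2 adds: "Information about SAEs and AESIs will be obtained through medical record review and visits".

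**The concern.** Vaccination is standard of care and not a study procedure (Section 5.4.1), so some first-dose enrollees may not receive dose 2 and the study cannot control this. The plan does not say what happens to them. Their later visits have no date, and neither does the end of their POM 5/6 and EOM 3/4 windows. They nevertheless meet the only defined cohort and so appear to count in the POM 5/6 table. That last step is an inference, because Section 7.2.2 states no denominator.

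Safety is the primary objective, and both outcomes are primary. An event treated outside the reviewed records could be missed in such a child because nobody is scheduled to ask. An event after dose 1 is also a plausible reason not to receive dose 2, so these children may not be a random subset; this is reasoning, not a figure from the documents. The comprehensive SAP promised in Section 7 can settle denominators, but it cannot recover contacts that were never made.

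**Working it through.** **1. The plan's own figure.** The Protocol Summary gives a participant duration of about 7 months. Inputs: a dose interval of 3 or 4 weeks (the trials described in Section 1), Visit 4 at Day 181 counting the dose-2 day as Day 1 (180 days later), and 365.25/12 = 30.44 days per month.

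- 3-week interval: (21 + 180)/30.44 = 6.6 months.
- 4-week interval: (28 + 180)/30.44 = 6.8 months.

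The stated duration reproduces for a first-dose enrollee who receives dose 2 at about 3 to 4 weeks. A booster enrollee has 180/30.44 = 5.9 months.

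**2. The schedule for a child without dose 2.**

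| SAE/AESI contact | Timed from | Date for this child |
|---|---|---|
| Visit 1a, Days 1-7 (+3) | dose 1 | by Day 7 to 10 |
| Visit 2, Day 1 (+3) | dose 2 | none |
| Visit 2a, Days 1-7 (+3) | dose 2 | none |
| Visit 3, Day 29 (+7) | dose 2 | none |
| Visit 4, Day 181 (+/-7) | dose 2 | none |

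**3. The literal gap, counting Day 1 as dose 1.**

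- To Day 181: 181 - 10 = 171 to 181 - 7 = 174 days without scheduled contact. Coverage is 7/181 = 4% to 10/181 = 6%.
- To Day 29: 29 - 10 = 19 to 29 - 7 = 22 days without scheduled contact. Coverage is 7/29 = 24% to 10/29 = 34%.

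The Day 29 figures are a worst case, because they assume that nobody calls about dose 2.

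**4. The gap if staff do call on the planned dose-2 date, within the +3 day window.**

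- 3-week interval: the call falls on Day 22 to 25, leaving 29 - 25 = 4 to 29 - 22 = 7 days to Day 29.
- 4-week interval: the call falls on Day 29 to 32, leaving none.
- To Day 181: 181 - 32 = 149 to 181 - 22 = 159 days remain (149/181 = 82% to 159/181 = 88%).

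**5. Which events.** Section 5.5 limits allergic-type AESIs to 7 days after a vaccination visit, so Visit 1a largely covers them. The gap concerns later SAEs, myocarditis or pericarditis, and MIS-C.

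**6. How many children.** The documents give neither the number of first-dose enrollees nor a rate of missed second doses. As an assumption for scale only, 80 to 320 first-dose enrollees and 2% to 20% missing dose 2 give 80 x 0.02 = 1.6 to 320 x 0.20 = 64 children. The top end requires every participant to be a first-dose enrollee, whereas the design also enrolls booster recipients.

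**The case against.** **Staff would find out.** Visit 1a confirms the next vaccine date, and Visit 2 may be a phone contact or data review that starts by confirming dose 2 and records SAEs and AESIs. A missed dose would probably come to light at about 3 to 4 weeks. This stands as a likely practice, and it removes most of the Day 29 gap. It is not a written rule, since Visit 2 is nominally timed from dose 2. Nothing further would be scheduled after it, so most of the Day 181 gap remains.

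**Record review continues.** It runs throughout the study and is not tied to dose 2. The stated duration of about 7 months also has no dose anchor and gives some meaning to the enrollment period. SAEs involving hospitalization normally leave records. This stands too. A reader might infer that these children go unmonitored after Day 10, or that their SAEs will be missed. The documents do not support that: what is lost is scheduled contact, one of the two sources named in Section 8.2.

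**The Protocol Summary.** A reader might take it as promising every child 181 days of follow-up. Its 181 days carry the same dose-2 or booster anchor, so only Section 3.1 supports the Day 181 intent cleanly.

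**The SAP is still to come.** Ending the windows after a completed series is a legitimate definition, and the handling of partial series is ordinary SAP content. That answers the denominator question but not the absence of contacts.

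**Conclusion.** The gap is real and should be fixed. Taken literally, a first-dose enrollee who never receives dose 2 has scheduled SAE/AESI contact only to Day 7 to 10, with 171 to 174 of 181 days left to record review. If staff call on the planned dose-2 date, 149 to 159 days still remain, assuming the 3- to 4-week intervals in Section 1. Both counts assume that Day 181 in Section 3.1 runs from dose 1 for this child.

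Two further inferences are not supported. Events after dose 1 are not excluded from POM 5/6, because the windows run through a point after dose 2 and only their end lacks a date. No particular under-count follows either, because the documents give no rate of missed second doses, no late-event rate and no number of first-dose enrollees.

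**What to change.** - Anchor SAE/AESI follow-up, POM 5/6 and EOM 3/4 to the last study-observed COVID-19 dose actually received.
- If no dose 2 is recorded by the end of the Day 29 (+7) window after dose 1, which is Day 36, make the existing SAE/AESI phone or record-review contact then and ask whether dose 2 has been given. Repeat it at Day 181 (+/-7) after dose 1 if it still has not.
- If dose 2 is given later, the child moves to the dose-2 visit schedule.
- Align the Protocol Summary and the end of study, records release and surveillance period in Section 5.5 with Section 3.1.
- State that dose-1-only children count in the POM 5/6 table, and report their number and observed follow-up time.

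The Day 36 trigger avoids needless calls. With a 4-week interval, an on-time dose 2 falls on Day 1 + 28 = Day 29, and Visit 2 may record it up to Day 32.

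The cost is up to two extra contacts of an existing type per dose-1-only child, one for each child whose dose 2 comes after Day 36, and revised protocol and records-release wording. The change concerns data collection only and does not touch vaccination or care.
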